4. TREATMENT PLAN

4.1 Dose de-escalation Study Design

The study will use a 6+3 design with a goal of determining the recommended phase 2 dose. We will enroll a cohort of 6 subjects, with a 3 mg dose of intratumoral SD-101 and 560 mg dose of oral ibrutinib. The proposed initial dose of SD-101 is below the maximum tolerated dose as determined in previous trials, and there is extensive data regarding the safety of treatment with ibrutinib at the FDA-approved dose of 560 mg. Because no additional toxicity is anticipated with combination therapy of SD-101 and ibrutinib, the 6+3 dose de-escalation design will be employed, permitting rapid confirmation of the safety of the combination therapy and selection of the recommended phase 2 dose while still allowing detection of any unanticipated toxicity.

If 0 or 1 subjects out of the initial 6 subjects experience a DLT, we will chose this dosing as the recommended phase 2 dose level. If 2 out of 6 subjects experience a DLT, we will expand the

cohort and enroll an additional 3 subjects at the same dose level. If 3 out of 6-9 subjects in the initial dose cohort experience a DLT, then the dose de-escalation cohort -1 will accrue. This dose de-escalation cohort will be treated with 1 mg intratumoral SD-101 and 560 mg ibrutinib. If \leq 2 out of 6 subjects in the dose de-escalation cohort experience a DLT, then this dose will be considered the RP2D. If 3 or more subjects in the de-escalation cohort experience a DLT, the study will be stopped.

Table 1. Dose Escalation Plan

Cohort	Dose (mg)	Total Enrollment per Cohort	Dose Escalation Rules
-1	1 mg SD-101 560 mg ibrutinib	6	1 of 6 or 2 of 6 DLT, RP2D is established 3 of 6 DLT, trial is stopped
1	3 mg SD-101 560 mg ibrutinib	6-9	0 of 6 or 1 of 6 DLT, RP2D is established at this level 2 of 6 DLT, expand cohort to 9 subjects 2 of 9 DLT, RP2D is established at this level 3 of 6-9 DLT, decrease to dose level -1
Phase 2 Expansion	RP2D	15	If the incidence of study drug-related DLTs as defined previously equals or exceeds 33% of treated subjects at RP2D dose level 1, enrollment will be stopped for dose level 1, and enrollment of 15 subjects will begin at dose level -1. If the incidence of study drug-related DLTs equals or exceeds 33% of treated subjects at RP2D dose level -1, then the trial is stopped

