Phase 2 (SD-101 dose Cohort Expansion): Once the safety profile and tolerability of all doses tested has been characterized and the RP2D of SD-101 has been defined during the dose de-escalation phase of this trial, the RP2D dose cohort will be expanded by an additional 15 subjects. This will enable further characterization of the immunoregulatory activity and preliminary antitumor effects of this treatment regimen. The treatment schema for SD-101, RT and ibrutinib will remain the same as previously described.

Clinical safety monitoring of subjects enrolled during this additional Cohort Expansion portion of the study will be the same as conducted during the dose escalation portion of the study (ie, part 1). If the chosen RP2D is dose level 1 (3 mg SD-101) and the combined incidence of study drug-related DLTs of any kind (ie, Grade 3 injection site reaction, hematologic or non-hematologic DLT) is equal to or exceeds 33% of treated subjects at any point during treatment, this will prompt a halt in enrollment at that dose level. Enrollment of 15 subjects will then begin at the lower dose level of 1 mg SD-101. If the incidence of DLTs in the lower dose cohort equals or exceeds 33%, the trial will be stopped.

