6.3 Dose Modifications for Ibrutinib

Ibrutinib dose modifications may occur starting on Day 31. Interrupt ibrutinib therapy for any Grade 3 or greater non-hematological, Grade 3 or greater neutropenia with infection or fever, or Grade 4 hematological toxicities. Once the symptoms of the toxicity have resolved to Grade 1 or baseline (recovery), ibrutinib therapy may be reinitiated at the starting dose. If the toxicity reoccurs, reduce dose by one capsule (140 mg per day). A second reduction of dose by 140 mg may be considered as needed. If these toxicities persist or recur following two dose reductions, this will be considered a DLT. Doses of ibrutinib may be held for surgeries or procedures as listed below in Section 4.9.2. Dose of ibrutinib will be reduced by 140 mg daily if chronic treatment with a moderate CYP3A inhibitor is required (see Section 4.9.2).

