Medical and scientific judgment should be exercised in deciding whether expedited reporting is also appropriate in other situations, such as important medical events that may not be immediately life threatening or result in death or hospitalization but may jeopardize the subject

or may require intervention to prevent one of the other outcomes listed in the definition above. These should usually be considered serious.

NOTE: DEATH FOR ANY REASON SHOULD BE REPORTED AS A SERIOUS ADVERSE EVENT.

Hospitalization:

For reports of hospitalization, details of the sign, symptom or diagnosis which led to the hospitalization must be provided.

Any event requiring hospitalization or prolongation of hospitalization that occurs during the study must be reported as a serious adverse event, except hospitalizations for the following:

Hospitalizations not intended to treat an acute illness or adverse event (eg, social reasons such as pending placement in long-term care facility)

Surgery or procedure planned before entry into the study. [Note: Hospitalizations that were planned before the start of data collection and where the underlying condition for which the hospitalization was planned has not worsened will not be considered serious adverse events.

Any adverse event that results in a prolongation of the originally planned hospitalization is to be reported as a new serious adverse event.]

Life-threatening Conditions:

Disease progression should not be recorded as an adverse event or serious adverse event term; instead, signs and symptoms of clinical sequelae resulting from disease progression/lack of efficacy will be reported if they fulfill the serious adverse event definition.

Adverse Events of Special Interest:

Adverse events of special interest are events that Janssen Scientific Affairs, LLC is actively monitoring as a result of a previously identified signal (even if non-serious). These adverse events are:

- *Major Hemorrhage*

Major hemorrhage is defined as any hemorrhagic event that is Grade 3 or greater in severity or that results in 1 of the following: intraocular bleeding causing loss of vision, the need for a transfusion of 2 or more units of red cells or an equivalent amount of whole blood, hospitalization, or prolongation of hospitalization.

- *Intracranial Hemorrhage*

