Any intracranial hemorrhage adverse event, including subdural hematoma/hemorrhage, epidural hematoma/hemorrhage and intracerebral hemorrhage, of any grade severity, will be captured as an event of special interest.

- *Other Malignancies*

In addition to all routine AE reporting, all new malignant tumors, including solid tumors, skin malignancies and hematologic malignancies, are to be reported for the duration of study treatment and during any protocol-specified follow-up periods including post-progression follow-up for overall survival.

Unanticipated (Unlisted) Problem Involving Risks to Participants or Others (UPs):

Adverse Event that is:

Unexpected: Not in the consent form, investigator brochure, protocol, package insert, or label, or unexpected in its specificity, severity or frequency AND

Related to the research: Caused by, or probably caused by research activity. Events caused by progression of underlying disease are NOT related. If a device is involved; the event was caused by, or associated with the device AND caused harm or increased risk of harm: Involves harm to participants or others, or places participants or others at increased risk of harm.

Unlisted adverse events related to the drug ibrutinib:

An adverse event will be considered unlisted if the nature or severity is not consistent with the applicable product reference safety information. The expectedness of an adverse event will be determined by whether or not it is listed in the applicable product information.

<http://www.imbruvica.com/>

Product Quality Complaint (PQC):

A product quality compliant is defined as any suspicion of a product defect related to a potential quality issue during manufacturing, packaging, release testing, stability monitoring, dose preparation, storage or distribution of the product, or delivery system. Not all PQCs involve a subject. Lot and batch numbers are of high significance and need to be collected whenever available.

Examples of PQC include but not limited to:

- Functional Problem: eg, altered delivery rate in a controlled release product
- Physical Defect: eg, abnormal odor, broken or crushed tablets/capsules
- Potential Dosing Device Malfunction: eg, autoinjector button not working, needle detaching from syringe
- Suspected Contamination
- Suspected Counterfeit

7.3 Assessing Adverse Events:

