10.1.1 Dose-Limiting Toxicity Definition

DLTs are defined as:

Days 1-30:

- Any Grade 4 treatment-related toxicity;
- Any Grade ≥ 3 treatment related toxicity persisting despite adequate/maximal medical therapy and/or prophylaxis. [NOTE: Grade 3 or lower treatment related skin rash not requiring systemic steroid therapy or other immunosuppressive therapy or Severe (Grade 3) flu-like symptoms are not considered DLTs. Grade 3 rash may be treated by withholding ibrutinib and/or systemic corticosteroids for up to 7 days. If rash resolves or improves to Grade 1, subjects may be restarted at the same dose of ibrutinib. If Grade 3 rash recurs upon restarting ibrutinib, then this will be considered a DLT];
- Any Grade ≥ 3 non-hematologic study drug-related toxicity will be considered a dose-limiting toxicity
- Any Grade ≥ 3 hematological study drug-related toxicity
- Grade ≥ 3 treatment related clinical autoimmune reaction involving major organs, which are defined as liver, pancreas, lung, heart, kidney, bowel, bone marrow and CNS (including the eye) which does not resolve to baseline or Grade 1 within 6 weeks;
- Grade ≥ 3 Injection Site Reaction;

Days 31-731:

- Any Grade 4 treatment related non-hematologic toxicity;
- Any Grade ≥ 3 treatment related toxicity persisting despite adequate/maximal medical therapy and/or prophylaxis. [NOTE: Grade 3 or lower treatment related skin rash not requiring systemic steroid therapy or other immunosuppressive therapy or Severe (Grade 3) flu-like symptoms are not considered DLTs];
- Grade ≥ 3 treatment related clinical autoimmune reaction involving major organs, which are defined as liver, pancreas, lung, heart, kidney, bowel, bone marrow and CNS (including the eye) which does not resolve to baseline or Grade 1 within 6 weeks
- Any Grade ≥ 3 hematologic toxicity that persists despite protocol-defined dose-modification of ibrutinib. (see Section 4.1)

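### After Day 30, a sudden treatment-related death is not a DLT as written and is left out of the 33% halt rule, although a survived Grade 4 non-hematologic event counts

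*Combined protocol and SAP*

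**What the plan says.** Section 10.1.1 defines DLTs separately for two periods.

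- **Days 1-30.** The list includes every related hematologic toxicity of Grade 3 or above and, likewise, every Grade ≥ 3 "non-hematologic study drug-related toxicity will be considered a dose-limiting toxicity". Neither criterion carries a further condition.
- **Days 31-731.** Those two criteria are gone. The one unconditional criterion is "Any Grade 4 treatment related non-hematologic toxicity". The other three are Grade ≥ 3 with a condition: "treatment related toxicity persisting despite adequate/maximal medical therapy and/or prophylaxis"; a major-organ autoimmune reaction that has not settled within 6 weeks; and hematologic toxicity that continues after ibrutinib dose modification.

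The definition feeds the expansion halt rule in section 4.1. Table 1 reads "If the incidence of study drug-related DLTs as defined previously equals or exceeds 33% of treated subjects", and the text below it applies the rule when the combined incidence "is equal to or exceeds 33% of treated subjects at any point during treatment". At 3 mg SD-101, reaching the line halts that dose and moves enrolment to 1 mg. At 1 mg it stops the trial.

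No section states that a death, or a Grade 5 event, is a DLT. Deaths appear under safety reporting in section 7.2: "DEATH FOR ANY REASON SHOULD BE REPORTED AS A SERIOUS ADVERSE EVENT".

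**The concern.** The late list ranks outcomes the wrong way round. A non-hematologic event that nearly kills the subject is a DLT immediately; the same event, if it kills before treatment can be given, is not. The reversal is confined to non-hematologic toxicity, because a late Grade 4 hematologic toxicity counts only if it persists. A sudden hematologic death nevertheless also falls outside every late criterion.

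Table 1 ties the halt rule to the definition in 10.1.1, so the wording there decides what is counted. The late window is also where most of the exposure to daily ibrutinib lies. Section 7.2 foresees events of this kind: intracranial hemorrhage "of any grade severity, will be captured as an event of special interest". If such a death is left out, enrolment can continue at a dose whose true toxicity count has reached the limit.

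**Working it through.** **1. A sudden related death after Day 30 against each late criterion.** Section 10.1.2 grades by CTCAE v4.0. The documents do not print the scale; I take Grade 5 to mean death.

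| Late criterion (10.1.1) | Survived Grade 4 non-hematologic event | Sudden death, no earlier Grade 4 non-hematologic phase, no time for therapy |
|---|---|---|
| Grade 4, non-hematologic | Met | Not met (Grade 5) |
| Grade ≥ 3, persisting despite therapy and/or prophylaxis | Not needed | Not met: nothing was given for it to persist against |
| Grade ≥ 3 autoimmune, unresolved at 6 weeks | Not needed | Not met unless autoimmune and already prolonged |
| Grade ≥ 3 hematologic, persisting after dose modification | Does not apply | Not met: no dose modification took place |
| **Counted as a DLT** | **Yes** | **No** |

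Many late related deaths are still caught: those that follow treated, unresponsive toxicity, and those that pass through a Grade 4 non-hematologic phase. The gap is limited to sudden deaths.

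**2. Is Grade 4 used elsewhere as shorthand for 4 and above?** The Days 1-30 list also has a bare Grade 4 criterion, but its unconditional Grade ≥ 3 criteria cover a death anyway. Where higher grades are meant, the protocol says so, as in section 6.3: "Interrupt ibrutinib therapy for any Grade 3 or greater non-hematological".

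**3. Share of planned ibrutinib time after Day 30.** Ibrutinib starts on Day 10 and runs to Week 96 (96 × 7 = 672 days).

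- Weeks counted from Day 1: Days 31-672 out of Days 10-672 = 642/663 = 96.8%.
- 96 weeks counted from Day 10: 651/672 = 96.9%.

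**4. Effect of one missed event on the 33% rule.** The smallest count that triggers at n treated subjects is the smallest k with k/n ≥ 0.33.

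| Treated, n | Trigger, k/n | One event uncounted |
|---|---|---|
| 9 | 3/9 = 33.3% | 2/9 = 22.2% |
| 12 | 4/12 = 33.3% | 3/12 = 25.0% |
| 15 | 5/15 = 33.3% | 4/15 = 26.7% |
| 21 | 7/21 = 33.3% | 6/21 = 28.6% |

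In every row the missed event takes the count below the line. The same applies to phase 1b: two counted DLTs plus one uncounted death among 9 subjects reads as 2 of 9, which sets 3 mg as the RP2D, where 3 of 9 would send the trial to 1 mg.

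**5. How often this would change the decision.** Let p be the per-subject probability of a captured DLT and q that of an uncaught death. Both are assumptions; the documents give neither. For a single look at n subjects,

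P(decision changes) = P(captured < k) − P(captured + uncaught < k) = F(k−1; n, p) − F(k−1; n, p+q),

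where F is the binomial distribution function. With n = 12 and k = 4, for p = 0.25 and q = 0.02: F(3; 12, 0.25) − F(3; 12, 0.27) = 0.6488 − 0.5863 = 0.0625. The full set at n = 12:

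| p | q = 0.5% | q = 1% | q = 2% |
|---|---|---|---|
| 5% | 0.1% | 0.2% | 0.5% |
| 10% | 0.4% | 0.9% | 2.1% |
| 15% | 0.9% | 1.9% | 4.0% |
| 25% | 1.6% | 3.1% | 6.3% |

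For p of 15% to 25% and q of 0.5% to 2%, the ranges at other sizes are 1.1% to 5.6% (n = 9), 0.8% to 6.8% (n = 15) and 0.5% to 7.4% (n = 21).

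**The case against.** The strongest reply is that nobody would apply the text this way. A severity trigger is naturally read as a floor, so Grade 4 is very likely a slip for Grade ≥ 4, and an investigator or the DSMC would probably count the death. A fatal toxicity can also be said to have persisted, and the mention of prophylaxis may widen that criterion. This is fair as a forecast of conduct, but both readings depart from what is written. A stopping rule should not need its wording overridden at the moment it is applied.

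Second, deaths are already visible. Every death is an SAE, SAEs of Grade 3 and above go to the DSMC whatever their cause (7.4.2), and the trial may be stopped for unacceptable toxicity (4.11). All of that stands, and a sudden related death would probably prompt a review by itself. None of it adds the death to the DLT count.

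Third, reaching the line at 3 mg lowers only SD-101, whose injections normally end by Day 30, while ibrutinib stays at 560 mg. For a late bleed caused by ibrutinib, less SD-101 would not address the cause. That limits the benefit at the higher dose, and it means that ibrutinib exposure time is not a measure of the risk of an uncaught death. But the rule as written counts DLTs at any point during treatment, and at 1 mg its consequence is to stop the trial.

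Fourth, the probabilities rest on assumed rates. With a captured DLT rate of 5% to 10%, the figure at 12 subjects falls to between 0.1% and 2.1%. This stands, and it puts the effect at the small end if the combination is well tolerated.

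**Conclusion.** The concern holds. As written, a sudden treatment-related death on Days 31-731 is not a DLT and does not enter the 33% count, while a survived Grade 4 non-hematologic event does. The gap is narrow: it excludes deaths after treated, unresponsive toxicity and deaths that pass through a Grade 4 non-hematologic phase. It changes a decision only when the count is one below the line. At 12 treated subjects the probability is 0.9% to 6.3% with a captured DLT rate of 15% to 25%, or 0.1% to 2.1% with 5% to 10%, in both cases assuming an uncaught death rate of 0.5% to 2% and a single look. The effect is uncommon, but every error is in the unsafe direction. The text should be corrected because it defines the event that governs dose and halt decisions.

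**What to change.** In the Days 31-731 list of section 10.1.1:

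1. Change the non-hematologic criterion from Grade 4 to Grade ≥ 4.
2. Add a criterion that any treatment-related death (Grade 5), hematologic or non-hematologic, is a DLT.

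State in section 4.1 and Table 1 that the DLT count uses this definition. The second change is needed as well as the first, because the first alone leaves sudden hematologic deaths uncounted.

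The cost is a few lines of wording. No new data are needed, since every death is already reported as an SAE. The only downside is that the DLT count may be slightly higher.

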10.1.2 Measurement Methods

Dose-limiting toxicity will be assessed using CTCAE v4.0.

10.1.3 Measurement Time Points

Dose-limiting toxicity will be assessed continuously throughout the trial. Adverse event information will be collected at each visit. Safety labs will be collected on Days 9; 23; 37; week 12; and every 12 weeks thereafter until the final study visit.

10.2 Phase 2 - Primary Outcome Measure

The primary outcome measure for the phase 2 portion will be to evaluate the response rate of intratumoral SD-101 in combination with ibrutinib and radiation in subjects.

10.2.1 Relevant Subset

This outcome will be measured on any individual who has received at least one intratumoral injection of SD-101 at the recommended phase 2 dose level. This will include any subjects treated during the phase 1B portion who were treated at the recommended phase 2 dose level.

10.2.2 Response Definition

Tumor response rates (CR, PR) will be calculated based on the Lugano classification (51) for low-grade B-cell lymphomas.

Definition of Measurable and Non-Measurable Lesions

Measurable Lesions are lesions that can be accurately measured in two perpendicular diameters, with at least one diameter ≥ 20 mm and the other dimension ≥ 10 mm (10 mm x 10 mm for spiral CT). The area will be defined as the product of the largest diameter with its perpendicular. Skin lesions can be considered measurable.

Non-Measurable (evaluable) Lesions are all other lesions, including unidimensionally measurable disease and small lesions (lesions without at least one diameter ≥ 20 mm), and any of the following:

- Lesions occurring in a previously irradiated area (unless they are documented as new lesions since the completion of radiation therapy), bone lesions, leptomeningeal disease, ascites, pleural or pericardial effusion, lymphangitis cutis/pulmonis, abdominal masses that are not pathologically/cytologically confirmed and followed by imaging techniques and cystic lesions.
- All measurable and non-measurable lesions should be measured at screening and at the defined tumor assessment time points. Extra assessments may be performed, as clinically indicated, if there is a suspicion of progression.

Definition of Index/Non-Index Lesions

All measurable lesions, up to a maximum of **5 lesions per organ** and **10 lesions in total**, should be identified as *index* lesions to be measured and recorded on the medical record at Screening. The *index* lesions should be representative of all involved organs. In addition, *index* lesions should be selected based on their size (lesions with the longest diameters), their suitability for accurate repeat assessment by imaging techniques, and how representative they are of the subject's tumor burden. At Screening, a sum of the products of diameters (SPD) for all *index* lesions will be calculated and considered the baseline sum of the products of diameters. Response criteria to be followed are listed below. The baseline sum will be used as the reference point to determine the objective tumor response of the *index* lesions at tumor assessment (TA).

Measurable lesions, other than *index* lesions, and all sites of non-measurable disease, will be identified as *non-index* lesions. *Non-index* lesions will be recorded on the medical record and should be evaluated at the same assessment time points as the *index* lesions. In subsequent

assessments, *non-index* lesions will be recorded as “stable or decreased disease,” “absent,” or “progression.”

Definition of Response

Response will be based upon the Lugano Classification (Table 6). To better assess systemic responses, an additional response assessment will be reported which will exclude any index lesions which were within the irradiation field. Overall response will include both complete and partial responses.

Table 6. IRB-36750 response based upon the Lugano Classification

Response and Site	CT-Based Response
Complete	Complete radiologic response (all of the following)
Lymph nodes and extralymphatic sites	Target nodes/nodal masses must regress to ≤ 1.5 cm in LDi No extralymphatic sites of disease
Nonmeasured lesion	Absent
Organ enlargement	Regress to normal
New lesions	None
Bone marrow	Normal by morphology; if indeterminate, IHC negative
Partial	Partial remission (all of the following)
Lymph nodes and extralymphatic sites	$\geq 50\%$ decrease in SPD of up to 6 target measurable nodes and extranodal sites When a lesion is too small to measure on CT, assign 5 mm \times 5 mm as the default value When no longer visible, 0 \times 0 mm For a node > 5 mm \times 5 mm, but smaller than normal, use actual measurement for calculation
Nonmeasured lesions	Absent/normal, regressed, but no increase
Organ enlargement	Spleen must have regressed by $> 50\%$ in length beyond normal
New lesions	None
Bone marrow	Not applicable
No response or stable disease	Stable disease
Target nodes/nodal masses, extranodal lesions	$< 50\%$ decrease from baseline in SPD of up to 6 dominant, measurable nodes and extranodal sites; no criteria for progressive disease are met
Nonmeasured lesions	No increase consistent with progression
Organ enlargement	No increase consistent with progression
New lesions	None
Bone marrow	Not applicable
Progressive disease	Progressive disease requires at least 1 of the following
Individual target nodes/nodal masses	PPD progression:

Table 6. IRB-36750 response based upon the Lugano Classification

Response and Site	CT-Based Response
Extranodal lesions	An individual node/lesion must be abnormal with:
	LDi > 1.5 cm and
	Increase by $\geq 50\%$ from PPD nadir and
	An increase in LDi or SDi from nadir
	0.5 cm for lesions ≤ 2 cm
	1.0 cm for lesions > 2 cm
	In the setting of splenomegaly, the splenic length must increase by $> 50\%$ of the extent of its prior increase beyond baseline (eg, a 15-cm spleen must increase to > 16 cm). If no prior splenomegaly, must increase by at least 2 cm from baseline
	New or recurrent splenomegaly
Nonmeasured lesions	New or clear progression of preexisting nonmeasured lesions
New lesions	Regrowth of previously resolved lesions
	A new node > 1.5 cm in any axis
	A new extranodal site > 1.0 cm in any axis; if < 1.0 cm in any axis, its presence must be unequivocal and must be attributable to lymphoma
	Assessable disease of any size unequivocally attributable to lymphoma
Bone marrow	New or recurrent involvement

Table 3. LDi, longest transverse diameter of a lesion; MRI, magnetic resonance imaging; PET, positron emission tomography; PPD, cross product of the LDi and perpendicular diameter; SDi, shortest axis perpendicular to the LDi; SPD, sum of the product of the perpendicular diameters for multiple lesions

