3.1 Inclusion Criteria

- 3.1.1 Biopsy-confirmed Grade 1 or 2, or 3A follicular lymphoma; mantle cell lymphoma; or marginal zone lymphoma. Subjects must have relapsed from or are refractory to prior therapy.
- 3.1.2 Subjects must have at least one site of disease that is accessible for intratumoral injection of SD-101 (*diameter $\geq 10\text{mm}$*), percutaneously.
- 3.1.3 Subjects must have at least one site of measurable disease (see Section 10.2.2 for definition of measurable disease) other than the injection site which is not included in the radiation field.
- 3.1.4 ECOG Performance Status of 0 or 1
- 3.1.5 Subjects must be 18 years of age or older.
- 3.1.6 Required values for initial laboratory tests:
 - a) Absolute neutrophil count (ANC) $\geq 1000/\text{mm}^3$ independent of growth factor support
 - b) Platelets: $\geq 100,000/\text{mm}^3$ or $\geq 50,000/\text{mm}^3$ if bone marrow involvement independent of transfusion support in either situation
 - c) Hemoglobin: $\geq 8 \text{ g/dL}$ (may be transfused)

- d) Creatinine: Creatinine clearance > 25 mL/min
- e) AST/ALT: $\leq 3 \times$ ULN
- f) Bilirubin: $\leq 1.5 \times$ ULN (except for subjects with Gilbert's Syndrome or of non-hepatic origin)

3.1.7 Must be at least 4 weeks since treatment with standard or investigational chemotherapy, biochemotherapy, major surgery, radiation, cytokine therapy, and 8 weeks since any monoclonal antibodies or immunotherapy, and recovered from any clinically significant toxicity experienced during treatment.

3.1.8 Women of childbearing potential and men who are sexually active must be practicing a highly effective method of birth control during and after the study (see Appendix E) consistent with local regulations regarding the use of birth control methods for subjects participating in clinical trials. Men must agree to not donate sperm during and after the study. For females, these restrictions apply for 1 month after the last dose of study drug. For males, these restrictions apply for 3 months after the last dose of study drug.

3.1.9 Women of childbearing potential must have a negative serum (beta-human chorionic gonadotropin [β -hCG]) or urine pregnancy test at Screening. Women who are pregnant or breastfeeding are ineligible for this study.

3.1.10 Life expectancy greater than 4 months.

3.1.11 Able to comply with the treatment schedule.

3.1.12 Ability to understand and the willingness to sign a written informed consent document.

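### A 10 to 15 mm node can be a target lesion although Table 6 accepts 1.5 cm or less as complete-response size, and Section 10.2.2 contradicts itself on whether that node is measurable

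*Combined protocol and SAP*

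**What the plan says.** Four parts of the protocol bear on this.

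- **Measurable disease (Section 10.2.2).** A lesion is measurable if one diameter reaches 20 mm and the other 10 mm, with a lower threshold given as "10 mm x 10 mm for spiral CT". The next paragraph lists as non-measurable all "small lesions (lesions without at least one diameter ≥ 20 mm"), and does not repeat the spiral CT allowance.
- **Index lesions (Section 10.2.2).** All measurable lesions, up to 5 per organ and 10 in total, "should be identified as *index* lesions to be measured and recorded on the medical record at Screening". There is a preference for large ones: "lesions should be selected based on their size (lesions with the longest diameters"). No minimum above the measurable threshold is given.
- **Response (Section 10.2.2, Table 6).** For CR, "Target nodes/nodal masses must regress to" 1.5 cm or less in LDi. All other CR rows must also be met: no extralymphatic disease, nonmeasured lesions absent, organs normal, no new lesions, marrow normal. For progression of a node, "An individual node/lesion must be abnormal with" an LDi above 1.5 cm, among other conditions. A second response assessment leaves out index lesions in the irradiated field, so as to show systemic effect.
- **Eligibility (Section 3.1).** Criterion 3.1.3 requires at least one site of measurable disease "other than the injection site which is not included in the radiation field", and refers to Section 10.2.2 for the definition. Criterion 3.1.2 requires an injectable site of only 10 mm or more.

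Section 10.2.3 makes CT the preferred imaging method, so the spiral CT allowance is likely to matter in practice.

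**The concern.** The baseline floor and the CR limit use different scales. Between 10 and 15 mm, a node is large enough to count as target disease and small enough to have CR size. For such a node the CR size row asks for almost no treatment effect.

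Overall response, CR plus partial response (PR), is the phase 2 primary outcome, and at least 21 subjects are planned at the recommended dose. The injected node is irradiated, and Section 2.2.3 puts local response to the same radiation schedule at 80 to 90% in recurrent follicular lymphoma. Evidence of a systemic effect must therefore come from disease outside the field. Criterion 3.1.3 asks for only one such site, so the additional systemic assessment could rest on a single node that was within the CR size limit at screening.

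The conflict inside Section 10.2.2 adds a second problem. Two readers following different sentences would treat the same node in opposite ways, both for eligibility and for CR.

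**Working it through.** I take Table 6's target nodes to be the index lesions of Section 10.2.2; the plan uses both terms without distinguishing them.

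**1. Sizes side by side**

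| Baseline node (mm) | Measurable by the spiral CT clause | Measurable by the 20 mm sentence | LDi within the CR limit (15 mm) before treatment |
|---|---|---|---|
| 10 x 10 | yes | no | yes |
| 12 x 10 | yes | no | yes |
| 15 x 15 | yes | no | yes |
| 20 x 10 | yes | yes | no |

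The overlap exists only under the spiral CT clause. Under the 20 x 10 mm rule every target node starts above 15 mm and must shrink appreciably.

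**2. What the CR row then asks**

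A 14 x 14 mm node that becomes 13 x 13 mm has regressed to 1.5 cm or less. The decrease in the product of diameters is 1 - (13 x 13)/(14 x 14) = 1 - 169/196 = 13.8%. PR needs at least 50%. On this node alone the change meets the CR size row but not the PR size row.

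**3. Conditions for it to affect a subject's response**

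- The 10 x 10 mm clause is applied.
- Every target node outside the field is 10 to 15 mm.
- Any other target node, including an injected one, is also at 1.5 cm or less at assessment. Under 3.1.2 it may have started there, or radiation may have brought it there.
- All other CR rows are met.

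**4. The same node under the 20 mm sentence**

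A 12 mm node is then non-measurable. It cannot satisfy 3.1.3, and it falls in the nonmeasured row, which requires absence for CR. The two readings give opposite results on eligibility and on CR.

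**5. Size**

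The plan's only power figure for this endpoint is 83.6% for 57% against 30% with n = 21 (Section 12.3.2). The one-sample normal approximation is Phi{[(p1 - p0)√n - z√(p0(1 - p0))] / √(p1(1 - p1))}. With p0 = 0.30, p1 = 0.57, n = 21 and z = 1.645 (one-sided 5%) it gives 83.56%, which matches. The present point does not depend on that figure.

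One subject counted as a responder who would otherwise be a non-responder adds 1/21 = 4.8 points. At n = 24, the upper planned number, it is 1/24 = 4.2 points.

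The documents do not give the number k of such subjects. As an illustration, assume that k of 21 count as CR through small target nodes, that the others respond at 30%, and that success means at least 11 of 21. That cut-off is mine; the plan states none for this comparison. The false-positive rate is P(X ≥ 11 - k) with X ~ Bin(21 - k, 0.30), and the expected response rate is [k + 0.30(21 - k)]/21.

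| k (assumed) | False-positive rate | Expected response rate |
|---|---|---|
| 0 | 2.6% | 30.0% |
| 1 | 4.8% | 33.3% |
| 2 | 8.4% | 36.7% |
| 3 | 14.1% | 40.0% |

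**The case against.** The strongest reply has four parts.

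- **The CR row requires regression.** An unchanged 12 mm node has not regressed, so a reader might wrongly infer that some subjects are already in CR at baseline. This stands against that inference. It does not close the gap, because no amount of regression is stated and 1 mm is enough.
- **The largest lesions are preferred as index lesions, and every CR row must be met.** One small node among larger ones produces no false CR. This limits how often the problem can arise. It gives no protection when the only nodes outside the field are small.
- **The 20 mm sentence may govern.** Then no 10 to 15 mm node is a target lesion. But nothing says that it overrides the spiral CT clause, so this is itself a reason to amend.
- **Small nodes can still fail.** A reader might infer that such a node cannot progress, or that progression is delayed. Table 6 does not support this. For lesions up to 2 cm it separately requires a 0.5 cm increase in one diameter. With both diameters at least 10 mm at baseline, that growth already takes LDi to 15 mm or more, so the 1.5 cm condition binds only when LDi ends at exactly 15 mm. A node that first shrinks and then regrows faces the same limit whatever its starting size. New lesions and nonmeasured progression also count.

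A reader might also infer that small nodes make PR too easy. That would be a feature of the relative 50% rule and not of this mismatch: 16 x 16 to 11 x 11 mm is also a decrease above 50% (1 - 121/256 = 53%).

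**Conclusion.** The mismatch is real, and nothing elsewhere in the documents removes it. Under the spiral CT clause, nodes of 10 to 15 mm can count toward CR in the primary endpoint after trivial shrinkage, and the additional systemic assessment can rest on one such node. Section 10.2.2 also contradicts itself on whether these nodes are measurable at all.

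The claim is that subjects can meet the node-size row in this way. The documents give no baseline lesion sizes, so they do not support saying that some subjects will. The 4.8 points per subject is a maximum: it requires that all CR rows are met and that the subject would otherwise be a non-responder. The false-positive rates depend on the assumed k and the illustrative cut-off. They show only that one or two such subjects would matter in a trial of 21.

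This should be corrected. It does not invalidate the endpoint.

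**What to change.** In Section 10.2.2:

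1. Require target (index) nodes to have a baseline LDi above 1.5 cm, consistent with Table 6, and treat smaller nodes as non-index.
2. Reconcile the sentence that makes lesions without a 20 mm diameter non-measurable. If it stays as it is, a node of 16 to 19 mm would be both a target lesion and non-measurable.
3. State how a non-index node of 1.5 cm or less is read in Table 6's nonmeasured row. Otherwise a stable 12 mm node could block CR, which is the opposite error.

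Criterion 3.1.3 already refers to Section 10.2.2 and needs no new cross-reference. Extranodal lesions need no separate floor for this purpose, because CR already requires that no extralymphatic disease remains.

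For subjects already enrolled, index lesions are measured at screening. Those whose out-of-field target nodes were all 1.5 cm or less can be listed, and the response rate reported with and without them.

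The cost is amendment wording. A few subjects whose only out-of-field disease is nodes of 10 to 15 mm would no longer qualify.
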